1.1 PROTOCOL SUMMARY AND/OR SCHEMA

Primary Objective This is a phase II study to assess the efficacy of short course daratumumab in multiple myeloma patients with minimal residual disease (MRD) positivity after induction therapy with/without consolidative autologous stem cell transplant (ASCT). Primary objective of the study will be to determine the rate of MRD negativity by the completion of 6 months of daratumumab therapy.

Secondary Objectives:

1. To assess the rate of sustained MRD negativity in the bone marrow.
2. To determine duration of MRD negativity
3. To compare MRD techniques of multi-parametric flow cytometry with next-generation sequencing and mass spectrometry.
4. To determine progression-free and overall survival

Exploratory Studies:

1. The gene panel MyType (or comparable next generation sequencing panel) will explore whether any mutations appear to be associated with response to therapy or toxicity associated with therapy.
2. MyType(or comparable next generation sequencing panel) will also be evaluated using samples at the time of progression of disease and will be compared to the pre-treatment baseline samples to explore whether pathways leading to emergence of resistance to the drug regimen can be identified.

Patient Population

The proposed study will enroll newly diagnosed multiple myeloma patients achieving a very good partial response (VGPR) or better with MRD positivity by flow cytometry after induction therapy with/without ASCT as well patients previously MRD negative for at least 3 months (after induction and consolidation therapy) and have turned MRD positive by flow cytometry with no evidence of progressive disease. All patients must be on standard of care lenalidomide maintenance for at least 6 months at the time of enrollment.

Study Design

- Single arm phase II trial of daratumumab for MRD positive multiple myeloma patients currently receiving standard of care lenalidomide maintenance therapy.
- Daratumumab is administered weekly for cycles 1 and 2 and bi-weekly for the remaining 4 cycles..
- Bone marrow biopsy will be obtained at baseline for confirmation of diagnosis and correlative studies. A follow-up bone marrow biopsy will be performed at the completion of treatment or at disease progression.

- Patients will also undergo evaluation for response at monthly intervals using traditional IMWG uniform response criteria (Kumar. et al. Lancet Oncology 2016) with serum and urine protein electrophoresis, immunofixation, and serum free light chains (FLC).
- Patients will continue standard of care lenalidomide maintenance during the protocol and after completing daratumumab as recommended by the treating physician.

Statistics

The primary objective of this trial is to determine whether treatment with daratumumab is associated with a substantial fraction of patients with MRD positive multiple myeloma converting to a MRD negative state as assessed by multicolor flow cytometry. Previously studies have reported that approximately 10% of patients will achieve deeper responses including MRD negativity after maintenance therapy with lenalidomide alone²⁹. The current study will be considered positive if the rate of MRD negativity is 30% or higher with daratumumab. This study will implement a Simon's two-stage minimax design to distinguish between an unpromising rate of 10% and a promising rate of 30%. The study is designed to have a type I error and a type II error of 0.10. The maximum sample size is 25 patients

Treatment Plan (see schema below)

- Cycles 1 and 2: Daratumumab 16mg/kg weekly as intravenous infusion (total duration: 8 weeks)
- Cycles 3-6: Daratumumab 16mg/kg once every 2 weeks as intravenous infusion (total duration: 16 weeks)
- Lenalidomide maintenance therapy to be administered as standard treatment to all patients. This is administered as 5-15 mg daily 21-28/28 day cycle.

Schema

MM patients with very good partial response (VGPR) or better after induction therapy with/without consolidative HDT/ASCT and MRD positive by bone marrow flow cytometry.

MM patients who were previously MRD negative after induction and consolidation and recently (within last 3 months) turned MRD positive by bone marrow flow cytometry.

Daratumumab 16mg/kg weekly for 8 weeks, followed by every 2 weeks for 16 weeks along with standard of care lenalidomide maintenance

2.1 OBJECTIVES AND SCIENTIFIC AIMS

Primary Objective:

This is a phase II study to assess the efficacy of short course daratumumab in multiple myeloma patients with minimal residual disease (MRD) positivity after induction therapy with/without consolidative autologous stem cell transplant (ASCT). Primary objective of the study will be to determine the rate of MRD negativity by the completion of 6 months of daratumumab therapy.

Secondary Objectives:

1. To assess the rate of sustained MRD negativity in the bone marrow).
2. To determine duration of MRD negativity
3. To compare MRD techniques of multi-parametric flow cytometry with next-generation sequencing and mass spectrometry.
4. To determine progression-free and overall survival

Exploratory Studies:

1. The gene panel MyType(or comparable next generation sequencing panel) will explore whether any mutations appear to be associated with response to therapy or toxicity associated with therapy.
2. MyType will (or comparable next generation sequencing panel) also be evaluated using samples at the time of progression of disease and will be compared to the pre-treatment baseline samples to explore whether pathways leading to emergence of resistance to the drug regimen can be identified.

3.0 BACKGROUND AND RATIONALE

3.1 Introduction

Multiple Myeloma and daratumumab

Multiple myeloma is characterized by clonal proliferation of malignant plasma cells in the bone marrow, affecting an estimated 22,000 people in the US annually¹; about 75,000 people are living with, or in remission from, multiple myeloma. Disease hallmarks include presence of monoclonal protein in serum or urine and features of end organ damage, including hypercalcemia, renal insufficiency, anemia, and bone lytic lesions². Multiple myeloma remains incurable with an estimated median survival of 3-4 years with conventional therapies and longer with newer agents^{3,4}.

CD38 is a 45-kD, type II transmembrane glycoprotein that associates with cell-surface receptors in lipid rafts, regulates cytoplasmic Ca²⁺ flux, and mediates signal transduction in lymphoid and myeloid cells^{5,6}. CD38 is highly and uniformly expressed on myeloma cells^{7,8} and is expressed at relatively low levels on normal lymphoid and myeloid cells and in some tissues of nonhematopoietic origin, which makes it a potential target in the treatment of myeloma⁶. Daratumumab (HuMax-CD38, Genmab), a human IgG1k monoclonal antibody, binds to a unique CD38 epitope⁹. Preclinical studies showed that daratumumab induced target-cell killing of CD38-expressing tumor cells by means of multiple mechanisms, including complement-mediated and antibody-dependent cell-mediated cytotoxic effects, antibody-dependent cellular phagocytosis, apoptosis^{9,10}, and to a lesser extent, inhibition of the enzymatic activity of CD38.

Early phase clinical trials have established the single agent activity and efficacy of this drug in patients with relapsed and/or refractory myeloma patients¹¹. Furthermore, the drug is fairly well tolerated with infusion related reactions being the most common adverse events¹¹. Daratumumab was approved by the FDA as monotherapy for patients with relapsed/refractory multiple myeloma in November 2015. This approval was based on a single arm phase trial with 106 patients that demonstrated an objective response rate of 29% with median duration of response of 7.4 months.

Daratumumab in Combination with Lenalidomide and Dexamethasone

More recently, Dimopoulos et al published the results of a Phase 3 study in patients with multiple myeloma with one or more prior lines of therapy randomized to receive lenalidomide (Revlimid[®]) and dexamethasone either alone or in combination with daratumumab¹². The estimated 12 month progression-free survival was 83.2% of patients receiving the three drug combination compared to 60.1% amongst patients receiving lenalidomide and dexamethasone only¹². Daratumumab was approved by the FDA in combination with lenalidomide and dexamethasone for patients with relapsed/refractory multiple myeloma in November 2016. However, daratumumab is not currently approved by the FDA for the indication under the current study i.e. patients with MRD positivity after induction therapy with/without consolidative HDT/ASCT.

Minimal Residual Disease Testing in Myeloma

In the past decade, multiple myeloma patients have reached deeper response rates with use of effective anti-myeloma therapeutics, immunomodulatory agents and proteasome inhibitors, approximating up to 75% patients achieving near-complete response (>90% decrease in monoclonal protein) or complete response (100% decrease in monoclonal protein). In general, improved therapeutics and deeper response rates have resulted in improved overall survival of multiple myeloma patients across most age groups. As a result, there has been an increasing interest for the development of sensitive assays to detect minimal residual disease (MRD) in treated MM patients¹³. In MM patients, MRD-negative status using multi-parametric flow cytometry (MFC) is associated with improved progression free survival and overall survival^{14,15}. Similar studies using next generation sequencing methods for MRD have also been shown to be associated with improved outcomes in MM MRD-negative patients.

Minimal Residual Disease Platforms

A recent survey including 30 major institutions in the US found major heterogeneity in MRD testing of multiple myeloma by flow cytometry¹⁶. In brief, there was considerable variation in the number of bone marrow cells analyzed (events) and number of abnormal plasma cells needed to define the presence of MRD, which affects maximum possible sensitivity. The maximum detection sensitivity ranged from 0.0005% to 0.02%, a 100-fold difference in sensitivity. Also, the variation in antibodies studied and definition of an abnormal plasma cell by flow cytometry affected the ability to differentiate normal from neoplastic plasma cells.

In 2015, the Department of Laboratory Medicine developed, validated and implemented the 10-color flow cytometry platform in collaboration with the Myeloma Service and the International Myeloma Foundation. The MSK single tube 10-color flow cytometry platform demonstrates similar results to Euroflow and is already in use under clinical practice¹⁷. Because there is currently no data available to compare the sensitivity of the MSK model and molecular MRD assays, as a secondary endpoint, we will compare our 10-color flow cytometry platform against next generation sequencing and mass spectrometry. These studies will help us to better understand and further develop details of various MRD methods.

3.2 Proposed Study Investigation with Correlative Studies

MRD negativity after induction (with/without consolidative ASCT) is an increasingly important outcome for patients with multiple myeloma. The management of low burden disease (VGPR or better) after initial induction and during maintenance therapy is unclear at this time. In the current study, we propose short course daratumumab for newly diagnosed MM patients with very good partial response (VGPR) or better after induction therapy with/without consolidative HDT/ASCT and MRD positive by bone marrow flow cytometry and for patients who were previously MRD negative after induction and consolidation and recently (within last 3 months) turned MRD positive (with no evidence of clinical progression) by bone marrow flow cytometry. All patients must be on standard of care lenalidomide maintenance for at least 6 months at the time of enrollment

All patients will receive a total of 24 weeks of daratumumab therapy (16 mg/kg intravenous infusion weekly for 8 weeks followed by every 2 weeks for 16 weeks) and continue standard of care lenalidomide maintenance therapy. Baseline studies will include bone marrow biopsy and aspirates with the first pulled bone marrow sample sent for multi-parametric flow cytometry as a priority sample to determine MRD status and determine eligibility. Upon completion of protocol therapy or when patients achieve sCR, patients will undergo a repeat bone marrow biopsy and aspirate for MRD assessment and correlative studies.

The study is powered to assess efficacy (as determined by rate of MRD negativity) of daratumumab in combination with standard of care lenalidomide maintenance amongst patients with low burden disease (i.e. MRD positivity). Our study is novel since no prior myeloma study has been designed to target MRD positive disease with the primary endpoint of achieving status MRD negativity. Secondary endpoints include evaluation of sustain MRD negativity, progression-free survival, overall-survival, and comparison of MRD platforms. Based on the rapidly evolving field with new powerful drugs, the anticipation is that MRD will become a new endpoint for future myeloma trials. MSK myeloma service is a global leader in this context.

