9.3 Monitoring

- 9.3.1 Routine labs (CBC, chemistry panel 14, LDH, magnesium, uric acid, phosphate) will be performed every 2 weeks for the first 2 cycles, then on day 1 for cycle 3-6, at end of therapy. Myeloma tests include serum protein electrophoresis, serum immunofixation, beta-2 microglobulin, quantitative immunoglobulins and serum free light chains assay will be performed at baseline, start of each cycle, at end of therapy. Routine labs, and myeloma labs can be performed 24 hrs in advance.
- 9.3.2 Patients will have clinic visits with H&P or standard progress notes assessing for toxicity/side effects at baseline, day 1 of each cycle, end of therapy, 1-month after end of therapy. Treatment window for day 1 of start of each cycle is +/- 7 days. Treatment window for intra-cycle daratumumab doses is +/- 2 days.
- 9.3.3 24-hr urine sample for protein electrophoresis (UPEP) and immunofixation will be performed at baseline
- 9.3.4 At CR/sCR or end of therapy, routine labs (CBC, chemistry panel 14, LDH, magnesium, uric acid, phosphate), myeloma specific tests - serum protein electrophoresis, serum immunofixation, beta-2 microglobulin, quantitative immunoglobulins and serum free light chains assay, lymphocyte subsets, 24-hr urine sample for protein electrophoresis (UPEP) and immunofixation to assess for monoclonal protein in the urine (Bence-Jones proteinuria). A bone marrow aspirate will also be performed to assess the status of minimal residual disease by flow cytometry (Sample sent will be the first bone marrow "pull"). Patient will have clinic visit (relevant clinical laboratories and H&P) 1 month after completing combination therapy to undergo assessment of toxicities/adverse events.

9.3.5 An Echocardiogram (2-D or strain echo) is optional at baseline (Please refer to Section 10.0).

Outside echocardiograms are permissible

9.3.6 Patients will have FDG-PET-CT at baseline, end of therapy or upon suspicion of progressive disease as clinically indicated.

9.3.7 PFS and OS data will be collected for patients.

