- k. Variations of +/- 7 days of scheduled visits are permitted.
- l. An echocardiogram (2-D or strain) will only be performed at baseline if the patient has had signs of significant cardiovascular disease. Outside echocardiograms are permissible.
- m. If screening labs are performed within 5 days of C1D1 they can be used for treatment on day 1.
- n. Variations of +/- 21 days of scheduled visits are permitted.
- o. Bone Marrow biopsy and aspirate will be required at time of serologic complete response. If patient is MRD negative on this bone

marrow one does not need to be completed at the end of treatment

Timepoints and potential analyses are listed below:

Bone Marrow

Sampling Time Points of Bone Marrow correlative studies

- a) Baseline
- b) End of therapy

*Patients undergoing MRD evaluation or End of study evaluation, the first pulled sample will be sent for Multiparametric flow cytometry and NGS MRD evaluation.

- Potential studies on the stored bone marrow samples may include but are not limited to the following:

Bone Marrow Aspirate/Biopsy

Pathology/Immunohistochemistry

Immunohistochemical staining will be assessed using immunohistochemistry markers such as CD 138, light chains, CD56 etc. Microenvironment interactions will also be assessed using various immunohistochemistry markers for osteoblasts, osteoclasts, stromal cells and proteasome components.

Minimal Residual Disease

Flow cytometry: Immunophenotyping of aberrant plasma cells by flow cytometry currently involves, but is not limited to, the use of the following reagents: CD138, CD19, CD45, CD38, and CD56. Characteristic changes in immunophenotypically abnormal plasma cells (CD38 bright and/or CD138 positive) include but are not limited to decreased or absent CD19 and CD45, decreased CD38, increased CD56, decreased CD27, decreased CD81, increased CD117. The first pulled bone marrow sample will be sent for multi-parametric flow cytometry as a priority. Samples will undergo MRD testing per MSK institutional practice, see section 12.0 for further methodology practice.

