12.1 CRITERIA FOR THERAPEUTIC RESPONSE/OUTCOME ASSESSMENT

Disease Parameters

Minimal Residual Disease

For patients undergoing MRD or end of study assessment, the first pulled bone marrow sample will be sent for multi-parametric flow cytometry as a priority. Flow cytometry based assay to rule out MRD in bone marrow aspirates and for MRD negative status using an assay with a sensitivity of at least 1 in 10^{-5} cells. Patients with <CR/sCR are considered MRD positive. We will use the MSKCC flow cytometry MRD method which is based on 10-colors in a single tube.¹⁶. The test demonstrates highly similar results when compared to the current Euroflow approach. This test is validated and already in clinical use at MSK. Immunophenotyping of aberrant plasma cells by flow cytometry currently involves, but is not limited to, the use of the following reagents: CD138, CD19, CD45, CD38, and CD56. Characteristic changes in immunophenotypically abnormal plasma cells (CD38 bright and/or CD138 positive) include but are not limited to decreased or absent CD19 and CD45, decreased CD38, increased CD56, decreased CD27, decreased CD81, increased CD117.

Traditional Response Criteria from International Myeloma Working Group Criteria for Multiple Myeloma²²

Evaluation of Response Criteria

- a) Stringent Complete Response (sCR)
 - o Complete Response as defined below plus: Normal FLC ratio and absence of clonal cells in bone marrow by immunohistochemistry or immunofluorescence (presence/absence of clonal cells is based on the kappa/ lambda ratio).
- b) Complete Response (CR)

- Negative immunofixation on the serum and urine and disappearance of any soft tissue plasmacytomas and $\leq 5\%$ plasma cells in bone marrow
- c) Very Good Partial Response (VGPR)
 - Serum and urine M-protein detectable by immunofixation but not on electrophoresis or 90% or greater reduction in serum M-protein plus urine M- protein level $<100\text{mg per 24h}$. If the serum and urine M-protein are unmeasurable, a $\geq 90\%$ decrease in the difference between involved and uninvolved FLC levels is required in place of the M- protein criteria.
- d) Partial Response (PR)
 - $\geq 50\%$ reduction in M protein and reduction in 24-h urinary M-protein by $\geq 90\%$ or to $< 200\text{ mg per 24h}$. If the serum and urine M-protein are unmeasurable, a $\geq 90\%$ difference between involved and uninvolved FLC levels is required in place of the M- protein criteria
- e) Stable Disease (SD)

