14.1 BIOSTATISTICS

Study Design/Primary Endpoints

This is a single arm phase II study designed to evaluate the efficacy of short course therapy with daratumumab, in multiple myeloma patients achieving a VGPR or better with MRD positive state while on lenalidomide maintenance for at least 6 months at the time of enrollment. The primary objective of this study is to determine the rate of conversion to MRD negativity by the completion of 6 cycles of treatment.

Rationale

The primary objective of this trial is to determine whether treatment with daratumumab is associated with a substantial fraction of patients with MRD positive multiple myeloma converting to a MRD negative state as assessed by multicolor flow cytometry. Previously studies have reported that approximately 10% of patients will achieve deeper responses including MRD negativity after maintenance therapy with lenalidomide alone¹⁸. The current study will be considered positive if the rate of MRD negativity is 30% or higher with daratumumab.

Power Calculations

This study will implement a Simon's two-stage minimax design to distinguish between an unpromising rate of 10% and a promising rate of 30%. The study is designed to have a type I error and a type II error of 0.10. The maximum sample size is 25 patients.

Primary analysis

In the first stage of the study, a total of 16 patients will accrue. If 2 or more patients achieve MRD negativity, additional 9 patients will accrue. If at the end of the study, 5 patients or more out the total 25 patients achieve MRD negativity, the short course daratumumab will be considered promising for future investigation.

Accrual will be held after the 16th patient if 2 or more patients have not yet achieved MRD negativity. We anticipate that one to two patients will accrue each month.

Analysis population for primary endpoint

All patients who receive at least one dose of daratumumab will be considered evaluable for the primary endpoint. Patients who do not have the end of therapy bone marrow for any reason and have not achieved MRD negativity at any point while on study will be considered a treatment failure.

Secondary endpoints:

1. To estimate the rate of sustained MRD negativity. Among patients achieving MRD negativity, sustained negativity is defined as remaining MRD negative at the 1-year post treatment

completion bone marrow biopsy. The proportion along with the 95% confidence interval will be estimated.

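### The trigger for the on-treatment marrow that feeds the primary endpoint is contradictory and partly circular, and the responder rule has no end date for patients without an end-of-therapy marrow

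*Combined protocol and SAP*

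**What the plan says.** The follow-up marrow is described in four ways:

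- **1.1 (summary, Study Design):** at completion of treatment or at progression; no response trigger.
- **3.2:** "Upon completion of protocol therapy or when patients achieve sCR, patients will undergo a repeat bone marrow biopsy and aspirate for MRD assessment".
- **9.3.4:** "At CR/sCR or end of therapy, routine labs", with the MRD marrow aspirate listed in the same paragraph. The schedule in 10.0 has a matching column for CR or sCR.
- **10.0, last lettered note:** "Bone Marrow biopsy and aspirate will be required at time of serologic complete response".

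Under 12.1, CR includes a limit on marrow plasma cells, and sCR adds "absence of clonal cells in bone marrow by immunohistochemistry or immunofluorescence". The same section treats any patient below CR/sCR as MRD positive. Section 6.2 admits patients in VGPR or better, so patients already in CR can enter.

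The notes to 10.0 make the end-of-study marrow optional (one note says not needed) after an early MRD-negative marrow. All other marrows stay mandatory.

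In 14.1 the objective is conversion within six cycles. Treated patients who lack the end-of-therapy marrow are failures if they "have not achieved MRD negativity at any point while on study".

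**The concern.** This marrow produces the primary endpoint, so the rule for when it is taken is part of the endpoint definition. A patient in CR but not sCR has an early marrow under 9.3.4 and the last note of 10.0, but not under 3.2. Under 1.1 nobody has one. The number of chances to be called MRD negative therefore depends on which section is followed.

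The extra chance works in one direction: an early negative can end the assessment, while an early positive is followed by another try. A patient who does not reach the trigger before end of therapy gets one look. The count is then judged against a fixed 10% null with a cut-off of 5 of 25. The start of MRD-negativity duration, a secondary endpoint, also depends on when the first negative marrow is taken.

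**Working it through.** **1. The triggers side by side**

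| Patient during treatment | 1.1 | 3.2 | 9.3.4 and schedule column | 10.0, last note |
|---|---|---|---|---|
| Serologic CR, marrow not yet done | no | cannot be known | cannot be known | yes |
| CR but not sCR | no | no | yes | yes |
| sCR | no | yes | yes | yes |
| Already in CR at entry | no | not stated | not stated | not stated |

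The first row shows the circularity. It affects the CR and sCR triggers, not the serologic one.

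**2. Possible sequences of results**

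- Early negative: the end-of-therapy marrow may be skipped.
- Early positive: the end-of-therapy marrow is mandatory, so there are two looks.
- No early marrow: one look.
- Early negative, then positive at end of therapy: no counting rule.
- No end-of-therapy marrow: not a failure if negative at any time on study. Completing daratumumab is not an off-study criterion in 13.1, so this has no end date.

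**3. The plan's own design**

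Inputs from 14.1: null 10%, target 30%; "The study is designed to have a type I error and a type II error of 0.10"; "The maximum sample size is 25 patients"; continue with 2 or more of 16; promising with 5 or more of 25.

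P(promising | p) = Σ over x = 2 to 16 of P(X₁ = x) · P(X₂ ≥ 5 − x), with X₁ ~ Bin(16, p) and X₂ ~ Bin(9, p).

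At p = 0.10:

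- x = 2: 0.2745 × 0.0530 = 0.0145
- x = 3: 0.1423 × 0.2252 = 0.0321
- x = 4: 0.0514 × 0.6126 = 0.0315
- x ≥ 5: 0.0170

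The sum is 0.0951. At p = 0.30 the same formula gives 0.9030. The stated design reproduces, so the sample size contains no arithmetic error.

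**4. Illustration of the extra look**

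Assumptions, none in the documents: one look gives the 10% null; a share f of patients has one extra look; that look calls a fraction q of otherwise positive patients negative.

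Null rate = 0.10 + f × 0.90 × q

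| f | q | Null rate | Type I error |
|---|---|---|---|
| 0 | any | 0.1000 | 0.095 |
| 0.25 | 2% | 0.1045 | 0.110 |
| 0.25 | 5% | 0.1113 | 0.134 |
| 0.60 | 2% | 0.1108 | 0.132 |
| 0.60 | 5% | 0.1270 | 0.199 |

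For example, 0.10 + 0.60 × 0.90 × 0.05 = 0.127. These figures lie on the high side, because the formula gives every non-responder with an extra look a chance of a false negative, while 12.1 calls patients below CR/sCR positive whatever flow cytometry shows.

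**The case against.** The operative section is 10.0, and its serologic trigger needs no marrow. The CR/sCR wording elsewhere can be read as shorthand for it, 3.2 is rationale and 1.1 is a summary. Reaching CR suggests a new event, which would exclude patients already in CR at entry. The trial is run at one centre, which limits divergent readings. Counting conversions cumulatively up to end of therapy is a legitimate choice, and an early negative that persists adds no bias.

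Much of this stands. It shows that a workable trigger already exists, but not that the other sections agree with it. The shorthand reading and the exclusion of patients in CR at entry remain inferences, and the negative-then-positive case is still unaddressed.

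A reader might also infer that 14.1 accepts a negative at any time as success for everyone. It does not say so: the phrase sits only in the failure rule for patients without an end-of-therapy marrow, and the endpoint itself is bounded by six cycles. That early negatives count is inferred from that bound, this rule and the waived marrow. The open window also has little to act on. The schedule shows no marrow after end of therapy, and the 1-year marrow in 14.1 is used among patients who have already converted.

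**Conclusion.** The point holds as a defect of endpoint definition and assessment schedule. The triggers conflict, two of them are circular, patients in CR at entry are not addressed, an early negative followed by a positive has no rule, and the failure rule lacks an end date for one subgroup.

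The effect on type I error cannot be derived from the documents. Under the assumed f = 0.60 and q = 2% to 5%, it rises from 0.095 to about 0.13 to 0.20, and these are upper-side figures. A reader might infer a far larger inflation by applying the same q to the single planned look as well. That gives 0.160 (2%) and 0.285 (5%) with no extra look at all, and 0.206 and 0.419 at f = 0.60. Most of that rise has nothing to do with the trigger, and the 10% null is itself based on reported rates, so the documents do not support attributing those figures to this problem.

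**What to change.** 1. Reconcile 1.1, 3.2, 9.3.4 and 10.0 to one trigger that can be known before the marrow, such as the serologic CR wording already in the last note of 10.0. State how it applies to patients in serologic CR at screening.
2. In 14.1, replace "have not achieved MRD negativity at any point while on study" with wording such as: *have had no MRD-negative result on any protocol marrow up to the end-of-therapy visit (+21 days)*. The 21 days match the marrow window in the notes to 10.0. State how an early negative followed by a positive end-of-therapy marrow is counted.
3. Add a sensitivity analysis over all treated patients: use the end-of-therapy marrow where it was done, carry forward an early negative where that marrow was waived, and count other missing marrows as failures. Restricting it to patients with an end-of-therapy marrow would selectively drop early successes.

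The cost is wording and one tabulation, with the sample size and cut-offs unchanged. A rare late conversion would no longer count. One trigger makes the number of looks predictable but does not make it equal across patients.
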